**Figure 1: Overall Study Design**

\*2 weeks for pump-experienced participants at baseline and 4 weeks for pump-naïve participants at baseline.

\*\*Visits 7 through 14 for pregnancy care and study follow-up.

Abbreviations: CGM, continuous glucose monitor; HCL, hybrid closed-loop insulin therapy; SAPT, sensor-augmented pump therapy

Women meeting the above criteria will be trained to start SAPT mode with the Medtronic Minimed 670G insulin pump and Guardian CGM and will continue SAPT mode throughout the remainder of the 1st trimester of pregnancy. Insulin adjustments will be made every 1-7 days for the first 2 weeks. Frequency of insulin adjustments will be guided by participant experience with pump therapy, glucose levels, level of insulin sensitivity, and willingness to contact study staff to ask for assistance, where (in general) women with less pump experience, a larger-than-expected number of glucose levels above or below ADA targets, dramatic insulin sensitivity, and unwilling to proactively contact study staff for assistance will be contacted more frequently for pump follow-up and adjustments as necessary. Women will be counseled on the maternal and fetal health risks in pregnancies associated with T1D, on the ability to reduce these risks with optimal glycemic control, on

the ADA-recommended targets for glycemic control (HbA1c <6.5% prior to conception/1st trimester, HbA1c <6% as pregnancy progresses, fasting glucose target <95 mg/dL, 1-hour postprandial glucose target <140 mg/dL, and 2-hour postprandial glucose target <120 mg/dL if these can be achieved without significant hypoglycemia), and on the need for multidisciplinary care in pregnancy (diabetes expert, CDE, RD, RN, social worker, high-risk OB, eye provider, and other specialists as needed). Women with hypoglycemia unawareness will be given modified glycemic targets per ADA guidelines and the discretion of the clinical investigator. Women will be counseled on their individualized gestational weight gain goals based on guidelines from the Institute of Medicine and the American College of Gynecology, their body mass indices, lifestyle, and stage of pregnancy. They will be advised to contact the study team or study clinicians as needed to trouble shoot (e.g., for further pump adjustments, for re-training about using the 670G system, etc.) and to report AEs and SAEs throughout the duration of the study.

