At the beginning of the 2nd trimester, women will be randomized to HCL therapy or SAPT. Women who were on multiple daily injections at baseline will complete a minimum of 4 weeks of therapy in SAPT mode prior to being randomized. All women in the HCL arm will be trained on the HCL technology. For the first 2 weeks after training, women will be contacted daily for insulin adjustments (if applicable) and trouble-shooting of device wearing. Frequency of insulin adjustments will be guided by glucose levels, level of insulin resistance, and willingness to contact study staff to ask for assistance, where (in general) women with a larger-than-expected number of glucose levels above or below ADA targets, dramatic insulin resistance, and unwilling to proactively contact study staff for assistance will be contacted more frequently for pump follow-up and adjustments as necessary. For the HCL group, insulin adjustments will be changes to carbohydrate-to-insulin doses and/or active insulin time. For the SAPT group, insulin adjustments will be changes to basal rates, carbohydrate-to-insulin doses, correction factors, and/or active insulin time. The first 5 women in each arm of the study will be asked to complete 7-point profiles for 2 weeks after randomization. Women will attend research and clinic visits at the Barbara Davis Center and Ohio State University every 4 weeks for routine diabetes care in pregnancy, downloading of study devices, and outcomes measurements. CGM, glucose meter, and pump downloads will also be reviewed throughout the study to ensure compliance with treatment assignment and the study protocol. Insulin pump adjustments will be made at least once every 4 weeks at face-to-face clinic/research visits and every week in between face-to-face visits, as per routine clinical care. When recommendations for pump adjustments are made during the interim weekly remote monitoring, we will verify that participants correctly entered the new settings. Acceptable forms of verification will include, verbal or written confirmation of new pump settings by the participant, a new upload of settings in CareLink, sending screen shots or pictures of the new settings from the participant’s pump. Women will be contacted every week in between research visits to inquire about open- and closed-loop wear (HCL group) and for pump adjustments as needed (both groups) (See Table 2 and Figure 2). As per routine clinical care, we will recommend that women start low-dose aspirin therapy (81-162 mg orally daily) between 12 and 16 weeks gestations, to reduce the risk of preeclampsia, unless there is a contraindication to aspirin therapy. At the start of the 2nd and 3rd trimesters, women will be given handouts describing conditions of which they should be aware for that trimester (see appendix).

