We will assess safety of HCL therapy by collecting data about episodes of SH requiring the assistance of a 3rd party and time spent <54 mg/dL (SH range), DKA, and skin reactions throughout the study. After the first 5 participants in each group complete 2 weeks of therapy after randomization, we will analyze interim data to compare SMBG measurements for time in the American Diabetes Association's recommended pregnancy target ranges (fasting <95 mg/dL and 2-hour post-prandial <120 mg/dL) and compare groups (see Table 2). Bedtime values will be considered post-prandial if they are within 2 hours of a meal  $\pm$  30 minutes but will be considered fasting (pre-meal) if they are >3.5 hours after a meal. If the average fasting blood glucose levels are 20% higher and the average 2-hour post-prandial values are 20% higher in the HCL arm compared to the SAPT arm, this would be considered worsening of glycemic control in the HCL arm. In the event that these interim analyses demonstrate worsening of glycemic control in the HCL arm, the study would be suspended until further investigation into the safety of the participants is undertaken. After the first 5 participants in each group have completed the 2nd trimester, we will analyze the interim data and compare episodes of SH between groups to ensure no increased risk of SH with HCL therapy (see Table 1). Episodes of SH will be used for the interim analysis as SH events can be life-threatening for pregnant women and their fetuses.

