Consortium, where artificial pancreas projects include HCL therapy and closed-loop therapy, which is coordinated by the JAEB Center for Health Research. JAEB is an organization that conducts diabetes-related human clinical trials. This partnership allows investigators with artificial pancreas projects funded by JDRF to utilize resources from the JAEB Center for Health Research without added cost to the investigator. For this study, the JAEB Center for Health Research has provided feedback for the Investigational Device Exception application submitted to the Food and Drug Administration, feedback on the statistical analyses, and will work with the study PI and JDRF to form the DSMB. It will be notified immediately of severe adverse events (SAEs). It will review the details of the SAE and the study protocol to determine if the SAE was possibly, definitely, or not related to study procedures. It will advise the study PI of its determination and of corrective action that needs to take place (if at all). The DSMB will be notified of SAEs within 1 business day. They will review the details of the SAE and the study protocol to determine if the SAE was possibly, definitely, or not related to study procedures. It will advise the study PI of its determination and of corrective action that needs to take place (if at all). The study PI will manage and report the SAEs and adverse events (AEs) to the IRB. Additionally, the DSMB will conduct phone or video conference calls every quarter to every 6 months to review all the SAEs and AEs that have taken place. The DSMB will also review the planned interim analyses of data (severe hypoglycemic events) after the first trimester in the first 5 participants of each group.

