This study's risks are minimized by use of extensive inclusion and exclusion criteria and close monitoring of research subjects. The key personnel are qualified and experienced in all of the study procedures. The collaborators and consultants provide necessary expertise for ensuring the safety of subjects and the integrity of the study procedures. We will also use a volunteer Safety Officer to oversee the study's safety. The Safety Officer will be an independent investigator (not a member of the research team) with experience in similar clinical research. S/he will review reports of adverse events, recruitment and enrollment statistics (ethnicity and numbers of subjects disqualified, withdrawn, randomized, and who completed the study) every 6 months. This information will be reviewed during meetings with study investigators and recorded by the Safety Officer in meeting minutes. A Data and Safety Monitoring Board (DSMB) will also be established and led by the Safety Officer. The DSMB will be comprised of the Safety Officer (from the University of Colorado), and additional faculty members from outside the BDC or OSU who are selected by the JAEB Center for Health Research. It will be notified immediately of severe adverse events (SAEs). It will review the details of the SAE and the study protocol to determine if the SAE was possibly, definitely, or not related to study procedures. It will advise the study PI of its determination and of corrective action that needs to take place (if at all). The DSMB will be notified of SAEs within 1 business day. They will review the details of the SAE and the study protocol to determine if the SAE was possibly, definitely, or not related to study procedures. It will advise the study PI of its determination and of corrective action that needs to take place (if at all). The study PI will

manage and report the SAEs and AEs to the IRB. Study staff will also identify, evaluate, and report anticipated and unanticipated device-related AEs. Additionally, the DSMB will conduct phone or video conference calls every quarter to review all the SAEs and AEs that have taken place. The DSMB will also review the planned interim analyses of data (especially glucose <63 m/dL) after the first trimester in the first 5 participants of each group.

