#### F. Data Analysis Plan:

##### Statistical Analysis Plan:

Data will be blinded to the study statistician. For the **interim safety analysis**, after the first 5 participants in each group have completed the 1st trimester, we will analyze the interim data to compare episodes of SH between groups to ensure no increased risk of SH with HCL therapy. Episodes of SH will be used for the interim analysis as SH events can be life-threatening for pregnant women and their fetuses. If interim safety analyses demonstrate no increased harm in either group, then the statistician will remain blinded until the end of the study. If the interim safety analyses demonstrate increased harm in one group necessitating evaluation of whether the study should be stopped, then the statistician will be unblinded at that point.

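### The interim severe-hypoglycemia comparison has two conflicting times and no data cut, and on one reading it contains no assigned closed-loop exposure

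*Combined protocol and SAP*

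**What the plan says.** Four places describe an interim look at the first five women per group.

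- **IV.F, Statistical Analysis Plan:** "after the first 5 participants in each group have completed the 1 st trimester, we will analyze the interim data". The comparison is of SH episodes between groups, and its purpose is to check that HCL does not raise SH risk.
- **IV.C, Data and Safety Monitoring Plan:** the DSMB reviews the "planned interim analyses of data (severe hypoglycemic events) after the first trimester in the first 5 participants of each group".
- **IV.D, Safety Monitoring:** the DSMB reviews the "planned interim analyses of data (especially glucose <63 m/dL) after the first trimester in the first 5 participants of each group".
- **IV.C, safety paragraph just before the text on virtual visits:** "After the first 5 participants in each group have completed the 2 nd trimester, we will analyze the interim data". The comparison is again of SH episodes, with the same purpose and the same rationale as in IV.F.

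On treatment sequence, IV.C says that women who pass the run-in "will continue SAPT mode throughout the remainder of the 1 st trimester of pregnancy". It then says: "At the beginning of the 2 nd trimester, women will be randomized to HCL therapy or SAPT". Women on injections at baseline need at least 4 weeks in SAPT mode before randomization. The Study Device text has closed mode follow 5 days in open mode.

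The same IV.C safety paragraph contains a separate interim look, on fingerstick glucose, timed "After the first 5 participants in each group complete 2 weeks of therapy after randomization".

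**The concern.** The statistician and the DSMB cannot follow all four descriptions. The conflict also goes beyond a date. Before the 2nd trimester there are no randomized groups and no study-assigned HCL therapy, so a comparison of SH in data up to the end of the 1st trimester compares two sets of women on the same study therapy. It could be reported as showing no increased harm when it had not examined HCL at all. Section IV.F ties possible unblinding, and the evaluation of whether to stop, to this look.

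If all data on the trigger date were used instead, some HCL time would be included. It would be mixed with events from the 1st trimester, which the Risks text in IV.D singles out as the period of especially high SH risk. No section says which data enter, or excludes events before randomization. The aims do not settle the matter: section II frames the safety comparison in the 2nd and 3rd trimesters and post-partum, while the SH primary outcome in IV.A covers the whole of gestation.

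**Working it through.** The plan gives no alpha, boundary, power or event count for this look, so there is no stated figure to reproduce. The check sets the texts side by side and counts HCL exposure under each reading.

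**Step 1. One analysis, four descriptions.**

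| Section | Milestone, first 5 per group | Metric |
|---|---|---|
| IV.F Statistical Analysis Plan | end of 1st trimester | SH |
| IV.C Data and Safety Monitoring Plan | after 1st trimester | SH |
| IV.D Safety Monitoring | after 1st trimester | chiefly glucose <63 mg/dL |
| IV.C safety paragraph | end of 2nd trimester | SH |

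The IV.F and IV.C safety texts share the sample, purpose and rationale, so they describe the same comparison.

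**Step 2. Cut at each woman's own 1st-trimester milestone.** Earliest randomization = max(start of 2nd trimester, enrollment week + 1 week run-in + 2 or 4 weeks SAPT). Enrollment at weeks 4, 6, 8 and 11 was tried, with the 2nd trimester assumed to start at 12, 13 or 14 weeks. At entry in week 11 the second term is 11 + 1 + 2 = 14 weeks for pump users and 11 + 1 + 4 = 16 for injection users. Randomization never precedes the start of the 2nd trimester, so study-assigned HCL exposure is **0 woman-weeks**. The inclusion and exclusion criteria do not rule out earlier use of a woman's own closed-loop pump, hence the words study-assigned.

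**Step 3. All data at the calendar trigger.** Assumptions, not in the documents: randomizations are evenly spaced over 10 months (43.5 weeks; IV.C gives 10 months for screening), and the trigger is the randomization of the later arm's fifth woman. With 24 randomized (IV.B), spacing is 43.5/24 = 1.81 weeks. If the first ten split exactly 5:5, mean HCL time is ½ × (0 + 1 + … + 9) × 1.81 = 22.5 × 1.81 ≈ 41 woman-weeks. Simulation (20,000 runs) for other allocation methods, since none is stated:

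| Allocation, 24 randomized | No lag | 5-day open-mode lag |
|---|---|---|
| Exactly 5:5 in first ten | 40.7 | 37.6 |
| Blocks of 4 | 43.5 | 40.2 |
| Simple 1:1 | 58.8 (5th–95th percentile 29–109) | 55.2 |

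The range of means is therefore about **38–59**. Varying the number randomized from 20 to 28 (28 being the IV.C target after run-in) widens it to about 32–70.

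**Step 4. The 2nd-trimester milestone.** Assume the 2nd trimester ends at 28 weeks, randomization falls at 13–16 weeks and the lag is 0–5 days. Per woman: 28 − 16 − 0.7 = 11.3 to 28 − 13 = 15.0 weeks. For five women: **56–75 woman-weeks**.

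**Step 5. Women randomized by each time (24 planned).** The 1st-trimester trigger falls at about woman 10 (5:5 split) to 12 (simple 1:1; simulated mean 12.5, 5th–95th percentile 10–18). The 2nd-trimester milestone is 28 − 16 = 12 to 28 − 13 = 15 weeks later, so 12/1.81 ≈ 6.6 to 15/1.81 ≈ 8.3 more women: about 16–20 in total.

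**Step 6. Sensitivity of a 5 v 5 look.** Two-sided Fisher, women with SH: 2 v 0, p = 0.44; 3 v 0, p = 2 × 10/120 = 0.17; 4 v 0, p = 2 × 5/210 = 0.048.

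**The case against.** **The look is weak whatever its timing.** It takes 4 v 0 to reach p < 0.05. In the center's earlier CGM study (Preliminary Studies), 2 women had SH among 36 analyzed, 28 of them prospective. At that rate, 10 × 2/36 = 0.6 to 10 × 2/28 = 0.7 of ten women would have SH, and the chance of none is (34/36)^10 = 56% to (26/28)^10 = 48%. This stands. No alpha or formal boundary depends on the look, and the final analysis is unaffected. Low sensitivity is still no reason to leave undefined whether HCL is being examined.

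**SH is monitored in other ways.** Each SH is reported as an SAE, and "The DSMB will be notified of SAEs within 1 business day". The DSMB judges relatedness and meets quarterly at first. Table 5 has a rule for a single SH event related to the HCL system, one for three SH events from any cause in an individual, and one for seven in the total cohort across at least two women. These are real safeguards. However, the HCL-specific rule covers only listed device deficiencies, the study-level rule does not separate the arms, and the fingerstick interim looks for higher glucose. None compares SH between arms.

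**The zero-exposure result depends on one reading.** The IV.F wording may simply set a trigger, after which all accrued data are analyzed. That is a fair reading, and the 1st-trimester look need not be empty. The plan does not choose between the readings, and the calendar reading still mixes in pre-randomization events.

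**The exposure figures rest on assumed accrual and allocation.** They do, and the conflict itself needs no simulation. Nor is 16–20 women an upper limit. Under simple 1:1 allocation the trigger falls after woman 12 in 2 × 794/4096 = 39% of sequences, and 15 further weeks then take the total above 20.

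**Conclusion.** The concern holds. The current text gives two times and two metrics for one interim safety comparison and no data cut. Depending on choices the plan does not state, the 1st-trimester look holds either no study-assigned HCL time or several dozen woman-weeks diluted by earlier events. The zero follows from the protocol's own treatment sequence and does not depend on where in weeks 12–14 the 2nd trimester is taken to start. The non-zero figures depend on the accrual, allocation and gestational-age assumptions above. This is the only explicitly planned between-arm SH comparison before the final analysis, for a device the protocol says has never been studied in pregnancy. It has to be corrected before the look is carried out, even though a 5 v 5 comparison will remain weak evidence.

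**What to change.** Reconcile the Statistical Analysis Plan (IV.F), the IV.C safety paragraph, the Data and Safety Monitoring Plan and Safety Monitoring (IV.D) so that all four state the same:

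1. **Milestone**, falling after randomization and after HCL exposure has accrued. The IV.C safety paragraph already contains one.
2. **Metric**, either SH episodes or a named CGM measure, used in every section.
3. **Data cut**, stating whether data run to each woman's own milestone or to the calendar date of the trigger.
4. **Counting rule**, with the between-arm comparison restricted to events from randomization onward, as the fingerstick interim already is, and pre-randomization SH listed separately.

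The cost is wording in four places, with no extra women or procedures. If the 2nd-trimester time is kept, the look comes about 12–15 weeks later than the SAP now says. About 16–20 of 24 women would on average already be randomized, against 10–12 at the SAP's trigger, and more in some sequences under simple randomization. Until then SH on HCL would be covered by SAE and DSMB review and Table 5, and the protocol should say so.

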### **II. Hypotheses and Specific Aims:**

The PICLS (Pregnancy Intervention with a Closed-Loop System) Study is a two-center, prospective, 'open-label', single-blind, investigator-initiated randomized controlled pilot

study evaluating hybrid closed-loop (HCL) insulin delivery among pregnant women with T1D compared with sensor-augmented pump therapy (SAPT) throughout gestation and the first 6 weeks of the post-partum period at the Barbara Davis Center for Diabetes and Ohio State University. The HCL system being used is the Medtronic 670G system, which has been FDA-approved in non-pregnant populations but has never been studied in pregnancy.

**Specific Aim (SA) 1:** Evaluate safety of HCL therapy (Medtronic 670G with Guardian sensor) compared to SAPT in women with T1D throughout the 2nd and 3rd trimesters of gestation and the early post-partum period.

**Hypothesis SA 1.1:** We hypothesize that time spent with glucose <54 mg/dL will be the same or reduced among women using the HCL system compared to those using SAPT.

**Hypothesis SA 1.2:** We hypothesize that the episodes of diabetic ketoacidosis and rates of adverse skin reactions will be similar between groups.

**Specific Aim 2:** Evaluate indices of glucose control and fear of hypoglycemia in pregnant women with T1D using HCL therapy compared to those using SAPT throughout the 2nd and 3rd trimesters of gestation and in the early post-partum period.

**Hypothesis SA 2.1:** We hypothesize that HCL therapy will increase time spent in the glucose target range (63-140 mg/dL), reduce time spent in mild and more severe hypoglycemia (<63 mg/dL and <54 mg/dL, respectively), and reduce time spent in hyperglycemia (>140 mg/dL) over time compared to SAPT.

**Hypothesis SA 2.2:** We hypothesize that HCL therapy will reduce fear of hypoglycemia as measured by the Hypoglycemia Fear Survey, starting in the 1st trimester of pregnancy compared to SAPT.

**Specific Aim 3:** Evaluate quality of life and device acceptability in pregnant women with T1D using HCL therapy compared to those using SAPT throughout the 2nd and 3rd trimesters of gestation and in the early post-partum period.

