#### **IV. Research Methods**

##### **A. Outcome Measure(s):**

###### **Primary Outcomes:**

- 1) Safety of HCL therapy compared to SAPT in women with T1D throughout gestation and the early post-partum period assessed through episodes of severe hypoglycemia and time spent with glucose <54 mg/dL.
- 2) Indices of glucose control and fear of hypoglycemia in pregnant women with T1D using HCL or SAPT therapy throughout pregnancy and early post-partum. Indices of glucose control are time spent in the glucose target ranges <54 mg/dL and <63 mg/dL (hypoglycemia), 63-140 mg/dL (time in range), and >140 mg/dL and >180 mg/dL (hyperglycemia). Fear of hypoglycemia is assessed as behavior, worry, and total scores of fear of hypoglycemia determined by the Hypoglycemia Fear Survey.

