##### **C. Study Design and Research Methods**

Overview: This is a two-center, prospective, 'open-label', single-blind, investigator-initiated randomized controlled pilot study evaluating HCL insulin delivery among pregnant women with T1D compared with SAPT throughout the 2nd and 3rd trimesters of gestation and the first 6 weeks of the post-partum period at the BDC and Ohio State University. Each institution will obtain IRB approval separately. The statistician will be blinded to treatment assignment, but the participants and clinical research team will not.

[figure not shown]
Study Design: Up to 37 women will be screened in the 1st trimester of pregnancy ( $\leq 11$  weeks gestation) over 10 months. All subjects meeting the initial inclusion/exclusion criteria will be invited to sign informed consent and participate in the study. The consent form must be signed by all women who wish to participate in the study, however there are two optional consent procedures: (1) providing specimens (blood and urine) to be stored in a biorepository for future research studies and (2) providing permission to be contacted for other research studies in the future. Consent for the optional procedures will be voluntary and will not affect regular clinical care for participants in any way.

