To address **Specific Aim 1**, we will compare percent of time spent in the SH range of <54 mg/dL on CGM (primary outcome) using a non-inferiority t-test with a margin of 1%. Counts of DKA and adverse skin reactions (secondary outcomes) will be compared between groups (HCL vs. SAPT) using t-tests for normally distributed variables and Wilcoxon Rank-Sum test for non-normal variables. As the purpose of this study is to demonstrate that HCL has a similar safety profile compared to SAPT during pregnancy, we will use a non-inferiority test. As a secondary analysis of events such as SH, DKA, and skin reactions, we will account for potential differential follow-up times due to miscarriage, drop-out, and withdrawal using Poisson regression with an offset for follow-up time. To address **Specific Aim 2**, we will compare CGM glucose variables (primary outcomes for glucose variables will be time spent <54, <63, 63-140, >140, >180 mg/dL; secondary outcomes will be glucose SD, J index, HBGI, LBG, MAGE, and CONGAn) and fear of hypoglycemia score between groups (HCL vs. SAPT) using t-tests for normally distributed variables and Wilcoxon Rank-Sum test for non-normally distributed variables. We will examine the buckets of time spent in each range (hypoglycemia, in range, and hyperglycemia) by day and night, as well as day-to-day variation. Mean glucose variables and hypoglycemia fear scores will be compared during each trimester of pregnancy and 4-6 weeks post-partum using mixed models. To address **Specific Aim 3**, we will compare SF-36 scores, insulin device satisfaction and glucose device satisfaction by group (HCL vs. SAPT) using t-tests if scores are normally distributed and Wilcoxon Rank-Sum test if scores are non-normal. We will analyze changes in INSPIRE Questionnaire scores over time in the HCL group. **Specific Aim 4** is an exploratory aim, and for this aim we will examine rates of fetal loss, preeclampsia, cesarean section, LGA, and neonatal hypoglycemia using Chi-square tests. We will account for potential differential follow-up times due to miscarriage, drop-out, and withdrawal using Poisson regression with an offset for follow-up time as a sensitivity analysis, in addition to the proposed chi-square tests in the exploratory analyses of fetal loss, preeclampsia, Caesarean section, LGA, and neonatal hypoglycemia. We will use mixed models to analyze changes in repeated measures, such as glycemia variables and hypoglycemia fear scores by trimester. We will evaluate the percent of time spent in closed loop by trimester as a feasibility outcome that is important to the next step of a larger clinical trial with efficacy outcomes.

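### The primary outcome window is stated in two ways and never anchored at randomization

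*Combined protocol and SAP*

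**What the plan says.** **Wider window.** Under Primary Outcomes, safety is compared "throughout gestation and the early post-partum period assessed through episodes of severe hypoglycemia and time spent with glucose <54 mg/dL", and the second primary outcome (glucose indices and fear of hypoglycemia) covers all of pregnancy and early post-partum. The study description that opens section II compares the arms "throughout gestation and the first 6 weeks of the post-partum period at the Barbara Davis Center for Diabetes and Ohio State University".

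**Narrower window.** Specific Aim 1 compares the arms "throughout the 2 nd and 3 rd trimesters of gestation and the early post-partum period", and Aim 2 has the same limits. The Overview in section C has "throughout the 2 nd and 3 rd trimesters of gestation and the first 6 weeks of the post-partum period".

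**The tests.** In the Statistical Analysis Plan, "we will compare percent of time spent in the SH range of <54 mg/dL on CGM (primary outcome) using a non-inferiority t-test" is introduced as addressing Specific Aim 1, and the glucose and fear tests as addressing Aim 2. No start date is given. Event rates are to be analyzed "using Poisson regression with an offset for follow-up time", with no start of follow-up. The mixed models read: "Mean glucose variables and hypoglycemia fear scores will be compared during each trimester of pregnancy and 4-6 weeks post-partum using mixed models". Hypothesis SA 2.2 places the effect of HCL on fear from the 1st trimester onward.

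**Timing of randomization (section C).** All women first do a one-week CGM run-in, for which a pump is not required, and then use SAPT for the rest of the 1st trimester. Randomization is planned for the beginning of the 2nd trimester. Women on injections at baseline must first complete at least 4 weeks of SAPT.

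**The concern.** Before randomization there is no treatment contrast. If those weeks enter the outcome average, any true difference between arms shrinks toward zero. In the Aim 1 non-inferiority safety test this favors a pass when HCL is in fact worse; in the time-in-range comparison it costs power. The data to make this possible exist, because glycemic data are collected at every visit from run-in onward.

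The narrower window does not fully remove the problem. A calendar 2nd-trimester start is not the randomization date for a woman on injections who enrolls late. The mixed-model sentence and SA 2.2 also take in 1st-trimester time, and do not say whether those values are baseline or part of the arm comparison. Two analysts could use different windows and both claim to follow the plan.

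**Working it through.** **Inputs.** From Power and Sample Size Calculations: 10 women per group; SD of time <54 mg/dL 1.1%; one-sided alpha 0.025; time-in-range difference 3.3 h/day with SD 2.5 h/day. Margin: 1% in the Statistical Analysis Plan, 1.5% in the power section. That mismatch is a separate point, so both are carried here. From Table 2: randomization (visit 6) at study week 5-11, last visit at week 36-42.

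**The plan's own figures.** SE = 1.1 × √(2/10) = 0.492, df = 18. Noncentral-t power at a true difference of zero:
- margin 1.5%: 82.2% (9 per group gives 77.5%), so 10 per group for 80% power is reproduced;
- margin 1%: 48.6%.

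Time in range: 3.3/2.5 = 1.32 SD. The normal approximation gives 83.9% (stated 83%); the t-test gives 79.7%, used below.

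**Dilution.** Let f be the pre-randomization share of the averaged time. Assume no arm difference before randomization, equal weighting of weeks and an unchanged SD. If the true post-randomization excess equals the margin M, the averaged difference is M(1 − f). The chance of declaring non-inferiority is then the upper tail beyond 2.101 of a noncentral t with noncentrality M·f/0.492.

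*Calendar 2nd-trimester window.* Enrollment at 10-11 weeks + 1 week run-in + 4 weeks SAPT puts randomization at week 15-16. With the 2nd trimester assumed to start at week 13-14, such a woman carries 15 − 14 = 1 to 16 − 13 = 3 pre-randomization weeks. Post-randomization follow-up is 36 − 5 = 31 or 42 − 11 = 31 weeks, so f = 1/32 (3%) to 3/34 (9%).

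*Literal wider window.* f = 5/36 (14%) to 11/42 (26%).

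| Window | f | False NI, 1% margin | False NI, 1.5% margin | Time-in-range power, d = 1.32(1 − f) |
|---|---|---|---|---|
| From randomization | 0 | 2.5% | 2.5% | 80% |
| Calendar, every woman a late injection user | 1/32 | 2.9% | 3.1% | 77% |
| Same | 3/34 | 3.7% | 4.4% | 72% |
| Literal, all weeks pooled | 5/36 | 4.5% | 6.0% | 67% |
| Same | 11/42 | 7.3% | 11.4% | 54% |

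Pairing the Table 2 weeks crosswise (5/42 to 11/36, or 12-31%) gives 4.2-8.5%, 5.3-14.1% and 69-49%. The pairing in the table keeps post-randomization follow-up at 31 weeks.

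**Baseline adjustment.** Adjusting for a pre-randomization value with correlation r multiplies the SE by √(1 − r²) × √(1 + 1/(2n − 4)), with df = 17. The documents give no r.

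| r (assumed) | NI power, 1% | NI power, 1.5% | Time-in-range power |
|---|---|---|---|
| Unadjusted | 49% | 82% | 80% |
| 0 | 46% | 80% | 77% |
| 0.5 | 57% | 90% | 88% |

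Break-even is at about r = 0.26.

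**The case against.** The best defense is that the plan does supply a window. Its tests are introduced as addressing Aims 1 and 2, and those aims begin with the 2nd trimester, when randomization is planned. No woman uses study HCL before randomization, so the wider phrase may be loose description. This largely stands: it makes the narrower window the likely reading and the pooled figures a worst case. It does not settle the matter, because the wider phrase sits in the formal outcome list and the narrower one is a calendar period.

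Even the calendar bound is generous. Under Data Collection and Analyses, 33 of 43 women in the earlier study presented before 8 weeks. If enrollment is similar and all of the other 10/43 (23%) are injection users carrying 3/34, then f = 0.233 × 0.088 = 0.021, and false non-inferiority is about 2.7% (1% margin) or 2.9% (1.5% margin).

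Two stronger readings are tempting and are not supported:
- A reader might infer that the non-inferiority test leaves out post-partum, since its stated purpose is "to demonstrate that HCL has a similar safety profile compared to SAPT during pregnancy". That sentence explains why a non-inferiority test was chosen. The Aims, the outcome list and the overview all include post-partum.
- A reader might infer that a pre-randomization arm comparison is intended, since the Statistical Analysis Plan sets an interim comparison of severe hypoglycemia after the 1st trimester. Section C sets that look after the 2nd. This is a separate conflict over interim timing and says nothing about the primary window.

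It is also fair to say that baseline adjustment is not needed for validity. Unadjusted tests on post-randomization data are valid. The SAPT phase may last only 2 weeks for pump-experienced women and overlaps with training and frequent insulin adjustment, so a high correlation cannot be taken for granted.

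**Conclusion.** The inconsistency is real and should be corrected before analysis. No passage starts the primary tests at each woman's randomization date. On the likely calendar reading the consequence is small, bounded by 3.7% or 4.4% false non-inferiority against a nominal 2.5%. Only the literal wider window with all weeks pooled gives a material effect: 4.5-7.3% or 6.0-11.4%, and time-in-range power down from 80% to 67-54%. These figures rest on an unchanged SD, equal weighting of weeks, no arm difference before randomization and the Table 2 week ranges. They describe what the text permits and do not predict what the sponsor will do. The stated sample size is unaffected.

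**What to change.** 1. Count all between-arm CGM, fear and event outcomes, and the Poisson follow-up time, from each woman's randomization date to the post-partum visit. Analyze all time in that window as randomized, including time that the HCL arm spends in manual mode. Make the study description, the Aims, SA 2.2, Primary Outcomes, the Overview and the Statistical Analysis Plan agree.
2. In the mixed models use 1st-trimester values only as baseline, through a baseline term or a common-baseline constraint. Reword SA 2.2 as an effect after randomization.
3. As an inexpensive improvement, adjust the time <54 mg/dL and time-in-range comparisons for the CGM value collected during SAPT before randomization. Keep the planned unadjusted tests as sensitivity analyses.

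Items 1 and 2 cost wording only, with no new data or visits. Item 3 uses one degree of freedom. It loses power if the baseline correlation is below about 0.26, by about 3 points at zero correlation.
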